Thus, we will enroll between 100-200 participants in total. There may be overlap in the Protocol A and Protocol B participants. As previously stated, participants will be given the opportunity (optional) to participate in both Protocols A and B. (Thus, in the event that all participants complete both protocols, we will enroll only 100 total participants, i.e., 50 patients and 50 healthy controls).

This being the first study of its kind, it is difficult to do a formal power and sample size

analysis because we do not have a measure of effect size, but given previous similar studies and our usual rate of loss to follow up, we calculate we will need 50 participants per group for each protocol.

Our enrollment numbers take into account the likelihood of attrition. We will only be able to use data sets that are complete (i.e., data collected from sham, excitatory, and inhibitory TMS). However, we anticipate that a subset of enrolled participants will not be able to complete all three study visits within a protocol because of scheduling or other challenges. Though we aim to enroll up to 50 patients and 50 healthy controls per protocol, we expect that the number of participants on whom we have useable data will be smaller.

Inclusion Criteria:

Patients

- Men and women
- Ages 18-50 years
- Patients diagnosed with schizophrenia (SZ), schizoaffective disorder (SZA), or psychotic bipolar disorder (BP).
- On a stable psychiatric medication regimen for at least a month prior to and during study participation
- Have structural brain MRI data on file from previous participation in research within the McLean Hospital Schizophrenia and Bipolar Disorder Program
- Have clinical diagnostic data (Structured Clinical Interview for DSM-IV: SCID) on file from previous participation in research within the McLean Hospital Schizophrenia and Bipolar Disorder Program

Healthy Controls:

- Men and women
- Ages 18-50 years
- Without major psychiatric illness
- Have structural brain MRI data on file from previous participation in research within the McLean Hospital Schizophrenia and Bipolar Disorder Program

Exclusion Criteria:

Patients

- Any change in psychiatric medications within a month prior to and during study participation
- Legal or mental incompetency
- Intellectual disability
- Substance use disorder (abuse or dependence) with active use within the last 3 months
- Significant medical or neurological illness
- Prior neurosurgical procedure
- History of seizures

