As a means of assessing participants' understanding of what the study entails, we will conduct a one-on-one informed consent survey, which asks questions such as, "What illness is being studied in this project?" "Are there any risks to participating in this study?" and "Will you lose any of your benefits if you refuse to participate in this study?" If the participant is unable to answer the questions or demonstrates a lack of understanding, the investigator will review the details of the study again. The survey therefore serves to ensure that participants are actively engaged in the informed consent process. For each participant, we will re-administer the informed consent survey at the beginning of each visit, in order to ensure that the participant is capable of consent throughout the entire study. Participants who are unable to answer all 9 questions on the survey correctly even after additional information is provided will be excluded from the study.

We will acquire written informed consent for all participants using the IRB-approved consent form. All signed forms will be stored in a file cabinet in a locked office.

For individuals who wish to participate in the second protocol (e.g., Protocol B after completing Protocol A), we will take the necessary time to remind participants about the study procedures, risks, and benefits, and answer any questions they may have about the study. We will also re-evaluate whether participants continue to meet the eligibility criteria. However, because Protocols A and B are both part of this same IRB protocol, we will not maintain separate written informed consent forms for the two protocols.

Treatment assignment, and randomization

All subjects, including controls, will receive either cTBS (inhibitory), iTBS (excitatory), or sham TBS in each of the three visits. The order in which they receive a particular type of TMS will be randomized for each subject by the study staff prior to the first TMS administration. The investigators and the research coordinator will not be blinded to the randomized order, since all

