As part of the clinical evaluation, we will also ask female participants about and record the first date of their last menstrual period (LMP). Clinical symptoms and cognitive functioning can vary according to the phase of the menstrual period. We will evaluate what phase of the menstrual cycle a female participant is in at the time of each study visit so that we can potentially control for any associated confounding effects.

Similarly, nicotine is well-documented to affect cognitive functioning, and is an important variable to control for. Therefore, we will administer a Fagerstrom Test for Nicotine Dependence in all research participants. For individuals who are smokers, we will record the time of the participant's last cigarette prior to each study visit.

For all subjects, during each and every visit, urine toxicology screens will be used to assess for current substance use, and urine pregnancy tests in women of child-bearing age to determine if she is

pregnant (and thus is ineligible to participate in the study).

Scheduling of study visits

As mentioned before, this will be a cross-over design, in which participants will undergo excitatory, inhibitory, and sham TBS over three study visits, separated by at least 36 hours. The order in which participants receive excitatory vs. inhibitory vs. sham TMS will be randomized.

The effects of a single session of rTMS are acute and reversible, and usually recede in less than an hour. Nonetheless, the study visits will be separated by at least 36 hours in order to provide more than ample time for the brain to return to homeostatic balance and ensure that there are no potential residual TMS effects from the previous study visit.

If scheduling permits, participants may be able to complete all three study visits in as short as one week. However, to accommodate scheduling flexibility for research participants, we will allow up to two months for participants to complete all three study visits within a single protocol.

Participants will participate in one of two protocols, Protocol A (**Figure 2**) or Protocol B (**Figure 3**). The two protocols are identical except that they involve different time perception and executive function tasks. Specifically, the tasks in Protocol A are the interval discrimination task, flanker task and the N-back working memory task, while those in Protocol B are the repetitive finger tapping task and the multi-source interference task (MSIT).

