We will test for group differences in demographic and clinical variables using SPSS, using χ^2 and t-tests for ANOVA as appropriate. We will first measure the change (Δ) in each of the pre- and post-TMS assessments at each study visit: i.e. accuracy in time interval discrimination task, accuracy and reaction time (RT) in N-back working memory task, executive function in Flanker task accuracy and RT in repetitive finger tapping task, and accuracy and RT in MSIT. We will then run two-way ANOVA for each outcome measure, with diagnosis (patients vs. healthy controls) and the TMS type (excitatory, inhibitory, or sham) as independent variables. These models will include as covariates sex, age, handedness, medication load, and symptom severities (derived from the clinical scales scores: NAART, PANSS, YMRS, MADRS, PSYRATS, BRIEF-A, BIS-11, and the Fagerstrom Test).

D. Power analysis (e.g. sample size, evaluable subjects)

This is a pilot study. This being the first study of its kind, it is difficult to do a formal power and sample size analysis because we do not have a measure of effect size, but given previous similar studies and our usual rate of loss to follow up, we estimate we will need 50 participants per group for each protocol. Of primary interest to the study is the change (Δ) in outcome measures within the psychosis group. With 50 subjects in the psychosis group, we will have 80% power to detect an effect size of 0.35, which is a moderate effect.

VII. RISKS AND DISCOMFORTS:

Common risks of TMS procedure

Subject may feel twitching of the scalp muscles during stimulation and/or local discomfort (tapping sensation) under the coil. It is possible that the subject may feel a headache after the TMS measurement that is generally caused by keeping the head in the same position for a lengthy period of time and/or by stimulation of the scalp muscles and nerves by the TMS pulses. TMS may also induce nausea in some patients¹¹⁴. The headache or nausea, if present, is typically mild, disappears soon and can be treated by mild over-the-counter analgesics.

Although there are no reports suggesting increased risk for TMS during pregnancy, pregnant women are excluded from this study due to insufficient knowledge of the effects of the strong magnetic fields on the fetus.

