PROTOCOL TITLE

Cerebellar transcranial magnetic stimulation (TMS) in psychotic disorders: effect on time perception, executive function, and mood and psychotic symptoms

NCT Number: NCT02642029

Date: August 22, 2022

Statistical Analyses:

We will test for group differences in demographic and clinical variables using χ^2 and t-tests or ANOVA, as appropriate. To examine the effect of TBS conditions on symptoms (as measured by visual analog scale scores, which are not normally distributed), we will conduct the non-parametric Friedman's test. For all other outcome measures, we will use mixed model regressions with TMS condition (cTBS, iTBS, or sham TBS), time (pre-TMS, post-TMS), and the interaction of condition x time as the primary variables of interest. To test the association between performance on the interval discrimination task (IDT) and symptoms, we will run mixed model regression models with TMS condition and time in addition to symptom score as the primary variable of interest.

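### The all-three-conditions rule in Protocol section III is needed for Friedman's test but not for the SAP's mixed models, where it would discard attended visits for a modest loss of precision

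*Protocol*

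**What the plan says.** Protocol section III (Subject Selection), in explaining the enrolment numbers, states: "We will only be able to use data sets that are complete (i.e., data collected from sham, excitatory, and inhibitory TMS". It expects that some participants "will not be able to complete all three study visits within a protocol because of scheduling or other challenges", and adds: "we expect that the number of participants on whom we have useable data will be smaller". No non-completion rate is given. The Compensation subsection of section V says that every visit's data are needed for a causal interpretation, as the reason for paying a completion bonus.

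Protocol section VI.C computes change from the "pre- and post-TMS assessments at each study visit", so each attended visit yields its own change. The SAP uses Friedman's test for VAS symptoms. It then says: "For all other outcome measures, we will use mixed model regressions with TMS condition", with time and condition by time as the other terms, and it uses mixed models again to relate interval discrimination to symptoms. It defines no analysis set, names no random effects and does not mention the section III rule.

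The protocol also creates other routes to an incomplete set. Patients are excluded for "Any change in psychiatric medications within a month prior to and during study participation". On consent, "we will re-administer the informed consent survey at the beginning of each visit". And "during each and every visit, urine toxicology screens will be used to assess for current substance use, and urine pregnancy tests" are done, with pregnancy making a woman ineligible. Neither document says what happens to visits completed before such an exclusion.

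**The concern.** Friedman's test ranks three conditions within a participant, so a participant with one missing condition contributes nothing. A likelihood-based mixed model has no such limit. A patient who attends for sham and iTBS and then stops informs the iTBS-sham contrast directly, yet under section III that patient's data are unusable.

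Two things are at stake. The first is precision in a study that already expects fewer usable participants than it enrols. The second is the protection that an analysis of all visits can give if non-return turns out to be related to response. Because the SAP is silent, one analyst could drop the incomplete participants and another keep them, and that choice could be made after the results are known.

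**Working it through.** **Inputs.** From the documents: 50 participants per group, three conditions in random order, effect size 0.35 and 80% power for the patient group (section VI.D). Assumed: non-completion of 10%, 20% or 30%; the same chance of non-return after Visits 1 and 2; correlation *r* between a participant's visit changes of 0.1 to 0.7.

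**1. The plan's power figure.** For a within-patient contrast, power = Φ(d√n − z). With d = 0.35, n = 50 and one-sided 5%: Φ(2.475 − 1.645) = 79.7%, which matches the stated 80%. Two-sided 5% gives 69.7%. So the figure needs a one-sided test and all 50 patients analysed.

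**2. Visits discarded.** Let p be the non-completion proportion. The proportion returning each time is s = √(1 − p). Attended visits = 50(1 + s + s²); completers' visits = 150s².

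| Non-completion | s | Attended | Used under the rule | Discarded |
|---|---|---|---|---|
| 10% | 0.949 | 142.4 | 135 | 7.4 |
| 20% | 0.894 | 134.7 | 120 | 14.7 |
| 30% | 0.837 | 126.8 | 105 | 21.8 |

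**3. Precision with correlated visit changes.** For completers the contrast variance is 2σ²(1 − r)/n_c, where n_c is the number of completers. For all visits it is the matching element of (Σ XᵢᵀVᵢ⁻¹Xᵢ)⁻¹, where Vᵢ has 1 on the diagonal and r elsewhere. Variance ratio, completers to all visits:

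| r | 10% | 20% | 30% |
|---|---|---|---|
| 0.7 | 1.034 | 1.076 | 1.127 |
| 0.24 | 1.047 | 1.105 | 1.177 |
| 0.1 | 1.052 | 1.115 | 1.194 |

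At 20%, √1.076 = 1.037 and √1.115 = 1.056, so intervals are about 4-6% wider. On the power scale of step 1, 40 completers give 71.5%. All visits are worth 40 × 1.076 = 43.0 to 40 × 1.115 = 44.6 complete participants, or 74.2% to 75.6%.

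**4. Precision with a participant intercept only.** The condition-by-time estimate then equals ordinary least squares on visit changes, as if those changes were independent. With losses split equally after Visits 1 and 2, the same variance ratio at 10 / 20 / 30% is 1.044 / 1.099 / 1.171 for r = 0.24, but 0.976 / 0.959 / 0.953 for r = 0.7. In the second case completers are the more precise.

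**5. Bias.** Simulated crossovers used n = 50, true changes of +0.35 (iTBS), −0.35 (cTBS) and 0 (sham), and 20% non-completion. Non-return was logistic on the last observed change, with slope 2 or 1. The all-visits model had correlated changes. Entries are iTBS-sham / cTBS-sham; the Monte Carlo standard error is about 0.002.

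| Non-return depends on | Completers, slope 2 | Completers, slope 1 | All visits, slope 2 |
|---|---|---|---|
| Nothing (scheduling) | +0.351 / −0.351 | same (no dependence) | +0.351 / −0.351 |
| Response at any visit | +0.326 / −0.325 | +0.339 / −0.342 | +0.346 / −0.353 |
| Response at cTBS visits only | +0.352 / −0.216 | +0.346 / −0.265 | +0.351 / −0.350 |

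The any-visit attenuation is (0.35 − 0.326)/0.35 = 7% at slope 2, and 2-3% at slope 1. With no true effect it vanishes at slope 2 (0.000 / +0.001). The cTBS-only shift in cTBS-sham is 0.13 at slope 2 and about 0.08 at slope 1. With no true effect it is +0.131 and +0.081.

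A separate simulation, also at about 20% loss, let non-return depend on a trait that modifies the stimulation effect. Completer contrasts were 11-18% too small, and all-visits contrasts 5-12% too small.

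**The case against.** The best defence is that the section III sentence is enrolment-planning text, written alongside the ANOVA of section VI.C. The SAP replaced that ANOVA with mixed models and never applies the rule to them. The study calls itself a pilot with no designated endpoint, and intervals 4-6% wider at an assumed 20% loss are a small matter. This stands as to size, and it makes the harm conditional on the rule being carried over. It does not remove the ambiguity: the sentence is current text and nothing in the SAP displaces it.

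The Compensation wording could be read as a scientific reason for needing complete sets. As a reason for encouraging attendance it is sound, and it should be reconciled with section III. It does not make incomplete sets uninformative in a mixed model.

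The point about random effects stands in full. The SAP names none, and step 4 shows that keeping all visits does not improve precision under every specification.

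A reader might infer that the rule will bias the results, or that an all-visits model would remove any bias. The documents support neither reading. Scheduling is the only specific reason given for non-return, although the mention of other challenges leaves the question open. Subjects are blinded, and section V describes single-session effects as usually receding in under an hour. Worsening symptoms would be a plausible route to response-related loss, but symptoms are analysed by Friedman's test, where complete sets remain necessary. The handling of visits before an in-study exclusion is a separate question, although the same SAP statement can settle it.

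**Conclusion.** The concern holds in conditional form. The rule is right for the VAS analysis and unnecessary for the mixed models. If applied to them, it costs about 3-5%, 8-12% or 13-19% in contrast variance at 10%, 20% or 30% non-completion, compared with an all-visits model that correlates visit changes. That comparison rests on assumed loss rates and on correlations from 0.1 to 0.7, and it does not carry over to a model with a participant intercept only.

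Non-return unrelated to response causes no bias. Under assumed dependence on response at any visit, with 20% loss, completer contrasts shrink by about 2-7%, depending on the strength of that dependence. The cTBS-only shift of 0.08-0.13 is an extreme bound that nothing in the documents suggests. It should not be read as a forecast. An all-visits model with correlated changes reduces such bias, but does not fully remove it when a trait drives both non-return and response. The change is worth making because it is cheap and settles an open choice before analysis, not because serious distortion has been shown.

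**What to change.** In Protocol section III, limit the complete-data requirement to the Friedman analysis of VAS. Make clear that the Compensation wording in section V explains the completion bonus and does not define the analysis set.

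In the SAP, add a statement along these lines:

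> The mixed models include all randomised participants with at least one visit with pre- and post-TMS data, use all attended visits and are fitted by REML. Random effects are participant intercept, participant-by-time and visit within participant, so that pre-to-post changes correlate across a participant's visits. Three-visit completers are a sensitivity analysis. Attendance by visit and condition is reported by group.

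The same paragraph should say whether visits completed before an in-study exclusion are included. Period and period-by-time terms are an optional, separate refinement.

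The cost is a sentence or two in the protocol and a short SAP paragraph, with no extra data. There are two downsides. The main analysis then relies on data being missing at random, hence the completer sensitivity analysis. The fuller random-effects structure may also fail to converge, so a simpler fallback should be named in advance. One candidate is a model of visit changes with a participant random effect. In five simulated data sets, with matching period terms, it gave the same contrast as the fuller structure to four decimals.

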assessments pre- and post-TMS require input solely from the subjects. However, subjects will be blinded as to which mode of TMS they receive at each study visit. Sham TMS will use the exact same procedure with a sham coil, which is designed to induce the same nonspecific sensory effects of TMS (auditory and somatosensory activation) without inducing the neuromodulatory magnetic fields. At the end of each study visit, subjects will be asked to speculate on which mode of TMS (inhibitory, excitatory, or sham) they received as well as the degree of certainty of their judgment so that we can assess the potential contributions of subjects' expectations on their task performance.

V. STUDY PROCEDURES:

All subjects, including healthy controls, will undergo three visits at the MGH Laboratory for Neuropsychiatry and Neuromodulation in the Charlestown Navy Yard Campus, with at least 36 hours separating the visits.

The subject is free to withdraw from the study at any time simply by informing the investigators. Similarly, the investigators may decide to stop the study if the purposes of the study cannot be met (technical difficulties, new information on subject characteristics, etc.).

Summary of Study Procedures

The first visit will include the following procedures (for the second and third visits, the clinical characterization step will be skipped):

Patients:

- Consenting procedures (15-20 minutes)
- Clinical characterization (1-2 hours)
 - Positive and Negative Syndrome Scale (PANSS)
 - Young Mania Rating Scale (YMRS)
 - Montgomery-Asberg Depression Rating Scale (MADRS)
 - North American Adult Reading Test (NAART)
 - Psychotic Symptom Rating Scale: PSYRATS-AH
 - The Behavior Rating Inventory of Executive Function – Adult Form (BRIEF-A)
 - Barratt Impulsiveness Scale (Version 11; BIS-11)
 - Fagerstrom Test for Nicotine Dependence
- Urine toxicology/pregnancy screen (5 minutes)
- Baseline/pre-TMS assessments (15-20 minutes)
 - Interval discrimination task for Protocol A (or repetitive finger-tapping task for Protocol B)
 - N-back working memory task for Protocol A (or multi-source interference task (MSIT) for Protocol B)
 - Flanker task for Protocol A
 - Visual analog scales (VAS) to assess mood and psychotic symptoms
- Transcranial Magnetic Stimulation (TMS) (15 minutes)
 - Excitatory, inhibitory, or sham (order randomized)
- Post-TMS assessments (15-20 minutes)
 - Interval discrimination task for Protocol A (or repetitive finger-tapping task for Protocol B)

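### No balanced set of TMS orders is specified and no planned analysis fits visit, although Visit 1 differs from Visits 2 and 3; blocked sequences plus a visit term are a cheap improvement

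*Protocol*

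**What the plan says.** Protocol section IV (Treatment assignment, and randomization) states that the order of cTBS, iTBS and sham "will be randomized for each subject by the study staff prior to the first TMS administration". Section V (Scheduling of study visits) adds "The order in which participants receive excitatory vs. inhibitory vs. sham TMS will be randomized", and the TMS subsection repeats that the order is random. No set of sequences, block, stratification, allocation list or means of concealment is described in either document.

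Section IV continues: "The investigators and the research coordinator will not be blinded to the randomized order". The reason given is that "assessments pre- and post-TMS require input solely from the subjects".

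In section V (Summary of Study Procedures), Visit 1 includes one to two hours of clinical characterisation, listed ahead of the pre-TMS tasks; "for the second and third visits, the clinical characterization step will be skipped".

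For analysis, protocol section VI.C plans an ANOVA of the pre-to-post change on diagnosis and TMS type with covariates. The SAP plans mixed models with condition, time (pre, post) and their interaction, and Friedman's test for the visual analogue scales. None of these names visit, period or sequence.

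**The concern.** Visit 1 is the first exposure to the protocol's tasks and follows a long interview session that later visits lack. The content of that session also differs by group: symptom scales for patients, a diagnostic interview for controls. Learning or fatigue could therefore make the pre-to-post change at Visit 1 different from the change at Visits 2 and 3. If one condition falls on Visit 1 more often than another, part of that visit effect enters the iTBS-sham or cTBS-sham contrast in the sample actually analysed. It can also enter the patient-control difference in that contrast, which the protocol's ANOVA examines. No planned model removes it, and Friedman's test has no place for a visit term.

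**Working it through.** **The plan's own figure.** The documents give no figure for sequence balance. The only computable design figure is 80% power for an effect of 0.35 with 50 patients (protocol VI.D). With alpha 0.05 (assumed), a test of mean change gives Φ(0.35√50 − 1.645) = Φ(0.83) = 79.7% one-sided and Φ(0.35√50 − 1.960) = Φ(0.51) = 69.7% two-sided (67.9% with the t distribution). The stated figure reproduces only one-sided. Here 0.35 serves only as a yardstick.

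**Inputs.** Three conditions over three visits give six orders. There are 50 subjects per group per protocol (section III). Only complete sets are used, but no dropout rate is given, so 30 completers is an assumed lower case. The Visit 1 effect on the change, δ, is not in the documents; 0.25 to 0.5 SD of the change is assumed.

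**Imbalance under independent draws.** Let d be the number receiving iTBS at Visit 1 minus the number receiving sham there. Each subject contributes +1, 0 or −1 with probability 1/3 each, so SD(d) = √(2n/3).

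| | n = 50 | n = 30 |
|---|---|---|
| SD(d) | 5.8 | 4.5 |
| 8 or more apart | 19% | 9% |
| 10 or more apart | 10% | 3% |

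**Shift in the realised contrast** when visit is not fitted: δ × d / n.

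- n = 50: SD = 0.25 × 5.77/50 = 0.03 to 0.5 × 5.77/50 = 0.06.
- n = 50, δ = 0.5: the shift exceeds 0.05 when d is at least 6 in size (34%), and exceeds 0.10 when it is at least 11 (7%).
- n = 30, δ = 0.5: it exceeds 0.10 when d is at least 7 in size (15%).
- Patient-control difference in the contrast, 50 per group, δ = 0.5 in both: SD = √2 × 0.058 = 0.08, above 0.10 in about 20%.

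For scale, the contrast's own standard error at n = 50 with uncorrelated changes is √(2/50) = 0.20.

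**Variance.** Per subject, the iTBS-sham difference has variance 2(1 − ρ), where ρ is the correlation between visits' changes. Independent ordering adds δ² × 2/3 = 0.25 × 2/3 = 0.167 at δ = 0.5. That is 0.167/2 = 8% more at ρ = 0 and 0.167/1 = 17% more at ρ = 0.5, relative to balanced orders. Once visit is fitted, imbalance costs only about 2% of variance at n = 50 and 4% at n = 30.

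**Error rates** (simulated paired contrast, n = 50, two-sided 0.05, δ = 0.5, no visit term). Independent draws keep type I error close to 5%. Blocked orders bring it to roughly 4%, because the standard error still contains the visit effect that blocking has removed from the estimate. At a paired effect of 0.35, power is 64.5% with independent draws and 65.1% with blocks (ρ = 0), or 61.3% and 61.7% (ρ = 0.5). Blocking alone therefore gains about half a point. Recovering the 67.9% available with no visit effect requires visit in the model as well.

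**With blocks of six orders**, Visit 1 counts are equal at n = 48 or 54 and differ by at most 2 at n = 50, before dropout. If 20 of 50 drop out at random (assumption), d has SD 2.9, against √(2 × 30/3) = 4.5 for independent draws.

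**The case against.** Several stronger readings are tempting, and the documents do not support them.

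- **That the plan uses unbalanced randomisation.** It is silent. Randomising for each subject is compatible with drawing from a balanced list, so every imbalance figure above is conditional on independent draws. Figures 2 and 3 show one order, but their footnotes say that order is randomised.
- **That the results would be biased or falsely significant.** Under independent draws the visit effect averages to zero and is already in the standard error, so type I error holds.
- **That unblinded staff could choose or redraw orders.** The investigators and coordinator know the order, but the staff who randomise are not identified, and nothing suggests redrawing. Since every subject is scheduled for all three conditions and only complete sets are used, foreknowledge cannot steer better-prognosis subjects to one condition.

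The other side is also right that δ is assumed, and that analysing change, or condition by time, cancels any constant shift in level at Visit 1. Only an effect on the change itself remains. One qualification: the SAP does not say whether Friedman's test uses change or post-TMS scores, and with post-TMS scores a level shift would enter too. The patient-control figure applies to the protocol's ANOVA; the SAP model lists no diagnosis term.

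What remains is a gap in specification and a modest, avoidable loss of precision.

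**Conclusion.** The point holds as a cheap improvement. The method of generating orders is not specified, Visit 1 is structurally different, and no planned analysis accounts for visit. If orders are drawn independently and the Visit 1 change differs by 0.5 SD, the variance of the iTBS-sham contrast is about 8% to 17% larger than with balanced orders, and the realised contrast shifts by more than 0.10 SD in about 7% of trials with 50 subjects or 15% with 30. With a smaller Visit 1 effect the cost shrinks quickly; with none it vanishes. Validity of the tests is not in question. Most of the gain for the mixed models comes from fitting visit. Balanced orders matter most for Friedman's test, which cannot adjust.

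**What to change.** 1. In section IV, state that order is assigned from a pre-generated list of all six sequences in mixed permuted blocks of 6 and 12, separately for patients and controls and for Protocols A and B. Someone who does not run visits prepares the list, and each assignment is released after the Visit 1 eligibility checks.
2. In the SAP, add visit as a fixed effect to the mixed models, so that the standard error reflects the balance. Where pre and post scores are both modelled, include visit by time, since the concern is the change. Add visit to the protocol's ANOVA of change likewise. State which score Friedman's test uses.
3. Report condition-by-visit counts among completers in each group.

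For subjects already randomised, only the visit term and the counts apply; the documents do not give enrolment status.

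The cost is a short script and a stored list (REDCap is already used for the visual analogue scales), with no added visits or subjects. Blocks are partly predictable to unblinded staff, which matters little when every subject is to receive all conditions, and dropout partly erodes the balance.
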